8.2 Secondary Outcomes

The secondary outcomes will include the following:

a) Impact on shoulder range of motion

Shoulder range of motion will be measured in the following exercises: shoulder flexion; shoulder abduction and external shoulder rotation at 90 degrees of abduction.

b) Impact on Pain

Measured through the following question: "On a scale of 0 to 10, where 0 is no pain and 10 the worst pain imaginable, how would you rate your pain in the last 24 hours?"

c) Interest in undergoing surgery

Measured through the following question: "On a scale of 0 to 10, where 0 is not at all and 10 is extremely interested, how interested are you in undergoing shoulder surgery in the next 12 months"?

d) Medication consumption

Measured through the following questions:

- i. "Are you taking any medication for your shoulder pain?";
- ii. "If yes, on how many days in a week, on average, are you taking medication for your shoulder pain"

e) Impact on fear avoidance beliefs

Measured by: Patient-reported questionnaire (Fear Avoidance Beliefs Questionnaire- FABQ)

f) Impact on anxiety and depression

Measured by the General Anxiety Disorder-7 scale and Patient Health Questionnaire-9 scale

g) Impact on work productivity and activity impairment

Measured through Work Productivity and Activity Impairment Questionnaire: Specific Health Problem v2.0 (WPAI:SHP)

h) Satisfaction with social roles and discretional social activities

Measured through the Patient Reported Outcomes Measurement Information System Computerized Adaptive Test (PROMIS-CAT) scales: Ability to participate in social roles and activities (version 2.0) and satisfaction with social roles and activities (version 2.0).

i) Patient engagement

Measured through: g.1) adherence to exercise sessions; g.2) drop-out rates; g.3) treatment intensity (i.e. total number of exercise minutes)

j) Patient satisfaction

Measured through the Net Promoter Score, by asking participants the following question: "On a scale from 0 to 10, how likely are you to recommend this program to a friend or colleague?"

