16. STATISTICAL ANALYSIS PLAN

To assess differences in clinical and demographic variables of the patients allocated to the two study groups, independent samples t test or Mann–Whitney U test will be used for quantitative variables. For categorical variables, Chi-square test or Fisher's exact test will be used. Outcome analysis will be performed using both an intention to treat analysis and a per-protocol analysis.

The overall impact of the intervention on the primary and secondary outcomes will be assessed considering both the results at the 8-week assessment as well as change from baseline.

Differences between interventions will be evaluated using independent samples t test or Mann-Whitney U test. For non-normally distributed variables, the magnitude of the difference in the medians will be assessed using Hodges-Lehman estimator. Additionally, a repeated measures ANOVA will also be performed, with group as an independent factor and time as a within-subjects factor. When necessary, logarithmic transformation will be performed to obtain normally distributed variables. In all analysis, a significant level of 0.05 will be considered.

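### Yes/no medication use and drop-out have no effect measure suited to binary data, and baseline medication use is not used as a covariate; both can be put right at no cost

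*Combined protocol and SAP*

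**What the plan says.** Section 8.2 d) measures medication consumption by two linked questions. The first is yes/no: "Are you taking any medication for your shoulder pain". The second, put to those who answer yes, asks for a frequency: "If yes, on how many days in a week, on average, are you taking medication for your shoulder pain". Section 8.2 i) measures patient engagement by three metrics, one of which is "g.2) drop-out rates".

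Section 16 opens with a paragraph whose purpose is stated as "To assess differences in clinical and demographic variables of the patients allocated to the two study groups". It gives the t test or Mann-Whitney test for quantitative variables and then says "For categorical variables, Chi-square test or" Fisher's exact test. It also says that outcomes will be analysed both by intention to treat and per protocol.

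The next paragraph says that outcomes are assessed both at 8 weeks and as change from baseline. The paragraph on treatment comparison reads "Differences between interventions will be evaluated using independent samples t test" or the Mann-Whitney test. For non-normally distributed variables, "the magnitude of the difference in the medians will be assessed using Hodges-Lehman estimator". It adds a repeated measures ANOVA with group and time as factors.

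Section 16 names no risk difference, odds ratio, model for binary data or interval for a proportion, and no baseline covariate. Section 15 collects medication use at baseline through the electronic questionnaire.

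**The concern.** A yes/no answer and a drop-out indicator are 0/1 variables and cannot be normally distributed. Read as written, the treatment-comparison rule sends them to Mann-Whitney with a Hodges-Lehmann estimate. On 0/1 data that estimate is in effect 0 or plus/minus 1, so it cannot express a difference in proportions. A report could show a small p value next to an effect of zero.

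The chi-square/Fisher sentence does not close the gap. It most naturally covers the comparability of the allocated groups. If it is extended to outcomes, it supplies a p value with no effect size or interval.

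Medication use also has a baseline answer. The plan uses it by subtraction or through the ANOVA. For a binary item, entering it as a covariate is usually the more precise choice, and the data are already collected.

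**Working it through.** **Inputs.** Section 9 gives 40 per arm and 10% dropout, so 40 × 0.9 = 36 evaluable per arm. The plan states no rate for medication use or drop-out, so there is no figure of its own to reproduce. All rates below are assumptions.

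**1. Hodges-Lehmann on 0/1 data.** The estimate is the median of all 36 × 36 = 1,296 between-arm differences, each −1, 0 or +1.

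- 22 v 11 users: pairs equal to +1 number 22 × 25 = 550 (42.4%), pairs equal to −1 number 14 × 11 = 154, and the rest are 0. The median is **0**.
- 25 v 9 users: 25 × 27 = 675 pairs (52.1%) equal +1. The median is **1**, although the difference in proportions is 16/36 = 44 points.

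In general the estimate leaves 0 only if p1(1 − p2) ≥ 0.5. For a given difference d, that product is largest at p1 = (1 + d)/2, where it equals ((1 + d)/2)². At d = 0.30 it is 0.65² = 0.4225, below 0.5, so the estimate is 0 at every base rate. The threshold is d = 2√0.5 − 1 = 0.414. At 36 per arm the smallest observed difference that gives a non-zero value is 24 v 9 (41.7 points).

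**2. The same data as proportions.** For 22 v 11 of 36:

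- Risk difference = 0.611 − 0.306 = 0.306.
- SE = √(0.611 × 0.389/36 + 0.306 × 0.694/36) = 0.112.
- 95% CI = 0.306 ± 1.96 × 0.112, or 8.6 to 52.5 points.

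**3. P values for that table.** Mann-Whitney 0.0098, t test 0.0088, chi-square 0.0093, Fisher 0.017. The first three agree closely; Fisher is somewhat more conservative. The mean difference behind the t test is the risk difference itself.

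**4. The change score.** For a yes/no item it takes only the values −1, 0 and 1. If 0 of 40 stop in one arm and 12 of 40 in the other, the mean difference is 0.30 and Hodges-Lehmann is again 0.

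**5. Value of the baseline answer.** Simulation with 36 per arm, 60% users at baseline and 8,000 runs per row. The adjusted analysis is a linear model with robust SE. Each row gives about 48% v 30% using at 8 weeks; for the first, 0.6 × 0.75 + 0.4 × 0.08 = 0.482 and 0.6 × 0.45 + 0.4 × 0.08 = 0.302.

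| Using at week 8, arm A v arm B: baseline users; baseline non-users | Unadjusted | Change score | Adjusted for baseline |
|---|---|---|---|
| 75% v 45%; 8% v 8% (strong tracking) | 34% | 37% | 44% |
| 60% v 42%; 30% v 12% | 33% | 25% | 35% |
| 55% v 37%; 38% v 20% | 34% | 23% | 34% |
| 48% v 30%; 48% v 30% (no tracking) | 34% | 20% | 33% |

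Repeat runs moved entries by one or two points; rounded, the ranges are 32–34%, 20–37% and 33–45%. In the first row the SE is 0.115 unadjusted, 0.110 for the change score and 0.097 adjusted. In the last row it is 0.112, 0.162 and 0.113. With no true effect, the adjusted test rejected in 4.5% to 4.8% of runs.

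**The case against.** The strongest reply is that this is silence, not an error. The first paragraph of section 16 pairs one set of tests with quantitative variables and another with categorical ones. A sensible statistician would carry that over to outcomes, and section 13 assigns the analysis to an independent statistician. Nothing directs anyone to compute a median shift on yes/no answers. Much of this stands, and it rules out several stronger readings:

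- A reader might infer that the trial will report a zero effect. That follows only if the non-normal rule is applied literally; the t test route already yields the risk difference.
- A reader might infer that the tests are invalid. They are not; the p values nearly coincide.
- A reader might infer that baseline is ignored. Change from baseline and the repeated measures ANOVA both use it. What is missing is a baseline covariate, and this concerns medication use only, since drop-out has no baseline value.
- A reader might infer that two whole secondary outcomes are binary. Each item is one component. If non-users were scored as 0 days, consumption would be a 0–7 count, for which Mann-Whitney is reasonable, though the plan does not state that scoring.

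It is also fair that the trial was sized on QuickDASH, that power for medication use is below 50% in every scenario above, and that the gain rests on assumed tracking. What remains is that, even on the generous reading, chi-square or Fisher gives no effect size, and that subtracting baseline can cost precision where a covariate would not.

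**Conclusion.** The point holds as a limited, free improvement to two components of secondary outcomes. Section 16 names no effect measure that suits a proportion; its named estimate for non-normal data, taken literally, is 0 for any 30-point difference. Inference by p value is essentially unaffected.

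For medication use, adjustment for the baseline answer gives power of about 33–45%, against 32–34% for unadjusted 8-week status and 20–37% for the change score. These figures assume 36 per arm, 60% baseline use and an 18-point difference. The gain over unadjusted status is about 10 points if use tracks strongly and near zero if it tracks weakly; in the latter case the change score is clearly the worst of the three. The documents supply none of these rates. The primary outcome is not touched.

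**What to change.** Add to section 16:

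- Medication use (yes/no) at 8 weeks is reported as a risk difference between arms with 95% CI, adjusted for baseline use, by a logistic model with standardised risks or a linear model with robust SE. This replaces the change score for this item.
- Drop-out is reported as an unadjusted risk difference with 95% CI and Fisher's exact test.
- Both items are excluded from the Hodges-Lehmann and repeated measures ANOVA rule.

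The cost is a few sentences. The data are already collected, and neither sample size nor visits change.

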9. SAMPLE SIZE ESTIMATION

Sample size estimation calculations were performed taking into consideration the primary outcome measure – the QuickDASH. In a sample of 57 patients with shoulder tendon disorders treated with SWORD Health's medical device in the context of work-related conditions, the mean and standard deviation of the QuickDASH scale at baseline was of 59 and 19 points respectively. A Minimal Detectable Difference (MDD) of 11.2 points was considered, based on the psychometric properties of the scale.⁵⁶ Considering a power of 80%, a two-sided 0.05 significance level and a 10% dropout rate, 80 (40+40) patients would be necessary to detect a 11.2 points difference between the two groups.

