8. STUDY OUTCOMES

8.1 Primary Outcome

Impact on physical function and symptoms measured through the shortened Disabilities of the Arm, Shoulder and Hand questionnaire (QuickDASH) between baseline and 8 weeks.

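### Section 9's own inputs give about 70% power with 40 patients per arm, not the stated 80%

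*Combined protocol and SAP*

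**What the plan says.** Section 9 bases the calculation on the QuickDASH. From 57 patients with shoulder tendon disorders treated with the sponsor's device it reports that "the mean and standard deviation of the QuickDASH scale at baseline was of 59 and 19 points respectively". For the effect size it says: "A Minimal Detectable Difference (MDD) of 11.2 points was considered". It concludes: "Considering a power of 80%, a two-sided 0.05 significance level and a 10% dropout rate, 80 (40+40) patients would be necessary to detect" an 11.2-point difference between the groups. It gives no other SD, no correlation between baseline and follow-up, no covariate adjustment and no non-inferiority margin.

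Section 8.1 defines the primary outcome as QuickDASH "between baseline and 8 weeks". Section 16 assesses outcomes "considering both the results at the 8-week assessment as well as change from baseline". It compares the arms by unadjusted t test or Mann-Whitney U test and adds a repeated measures ANOVA. On the error rate it says only: "In all analysis, a significant level of 0.05 will be considered". Sidedness is stated in Section 9 alone.

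**The concern.** The power statement is the only justification for 80 patients. Section 9 contains every input needed to check it, and the result does not follow from them. The gap is 24 to 26 patients, too large for rounding or choice of software.

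A second weakness is that 19 is the spread of scores at baseline. The planned analyses use the week-8 score and the change from baseline, and either may have a different SD. Section 9 does not say that 19 is assumed to apply to them.

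This bears on how the result is read. Sections 1 and 6 hypothesise that the digital programme does no worse than conventional PT, while Section 16 only tests for differences. A non-significant result could be taken as support for the hypothesis. The chance of such a result when a true 11.2-point difference exists would be about 30%, against the 20% that Section 9 implies.

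**Working it through.** **Inputs, all from Section 9:** SD 19; difference 11.2; two-sided 0.05; power 80%; dropout 10%; 40 patients per arm. The standardised difference is 11.2/19 = 0.589.

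**Step 1. Try to reproduce 40 per arm.** By the normal approximation, n per arm = 2 × (z for alpha + z for power)² × SD² / difference².

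- 2 × (1.960 + 0.842)² × 19² / 11.2² = 45.2, so 46 evaluable per arm.
- 46/0.9 = 51.1, so 52 per arm and 104 in total.
- By t test the requirement is 46.2, so 47; 47/0.9 = 52.2, so 53 per arm and 106 in total.
- Leaving dropout out gives 2 × 46 = 92. Multiplying by 1.1 instead of dividing by 0.9 gives 46 × 1.1 = 50.6, so 51 per arm and 102 in total.

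None of these is 80.

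**Step 2. Power that 40 per arm gives.** The standard error of the difference is 19 × √(2/n), and power by the normal approximation is Φ(11.2/SE − 1.960).

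| Evaluable per arm | SE | 11.2/SE | Power (normal) | Power (t test) |
|---|---|---|---|---|
| 36 (40 less 10%) | 4.478 | 2.501 | 70.6% | 69.4% |
| 40 (no dropout) | 4.249 | 2.636 | 75.1% | 74.0% |

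**Step 3. What 36 per arm supports at 80% power, two-sided 0.05.**

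- Detectable difference with SD 19: 12.5 points (normal) or 12.7 (t).
- SD required for 11.2 points: 17.0 (normal) or 16.7 (t).

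**Step 4. Calculations that do return 40 per arm.** By the normal approximation there are two:

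- One-sided 0.05 at 80% power: 2 × (1.645 + 0.842)² × 361/125.44 = 35.6, so 36; 36/0.9 = 40.
- Two-sided 0.05 at 70% power: 35.5, so 36; 36/0.9 = 40.

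The first contradicts the stated sidedness and the second the stated power. By t test they need 36.3 and 36.5, so 37; 37/0.9 = 41.1, so 42 per arm. The documents do not say which calculation was run, so these are only possible sources.

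**Step 5. If the analysed quantity is not one with SD 19.** Assumption, not in the documents: SD 19 at both visits and correlation r between baseline and week 8.

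- Unadjusted change score: SD = 19 × √(2(1 − r)).
- Week-8 score adjusted for baseline: SD = 19 × √(1 − r²).

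| r | Change-score SD | Change-score power, 36 per arm (t) |
|---|---|---|
| 0.3 | 22.5 | 55% |
| 0.5 | 19.0 | 69% |
| 0.6 | 17.0 | 79% |
| 0.7 | 14.7 | 89% |

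The change score reaches 80% at r of about 0.61 (t). With adjustment for baseline, r = 0.5 gives SD 16.5 and 81% power (t, 69 degrees of freedom), and 80% needs r of about 0.475.

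**The case against.** The arithmetic is hard to contest, but four points can be put on the other side.

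- **SD 19 is only a baseline SD, so 70% is not established as the trial's power.** This stands as a limit on the figure: under the assumptions above, change-score power runs from 55% to 89%. It does not defend the 80%, because 19 is the only SD given and no correlation is stated.
- **The hypothesis is directional, and a one-sided 0.05 calculation gives exactly 40 per arm** (numerically the same as non-inferiority with a margin of 11.2). Mis-stated sidedness is a plausible explanation. But Section 9 specifies "a two-sided 0.05 significance level", sizes the trial to detect a difference and gives no margin. If a one-sided calculation was meant, Section 9 is still wrong as written.
- **Dropout in Section 14 is partly non-engagement, which need not mean a missing QuickDASH, and Section 16 plans an intention-to-treat analysis.** More than 36 per arm might therefore contribute. Against that, Section 15 excludes participants who do not complete the assessment forms. With all 40 analysed, power is still only 74% to 75%.
- **The repeated measures ANOVA might be more efficient.** Its power also depends on the within-patient correlation, which is not given, and Section 9 does not rely on it.

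**Conclusion.** The concern holds. The stated inputs do not support 80% power with 40 patients per arm. This is certain from Section 9 alone.

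The size of the shortfall is conditional. If SD 19 applies to the analysed quantity, if 10% of patients are lost and if the test is two-sided at 0.05, power is 71% (normal) or 69% (t). The risk of missing an 11.2-point difference is then 29% or 31%. The stated 80% would need 24 (normal) to 26 (t) more patients. If SD 19 does not apply, the true power may be lower or higher, and the documents do not settle which. The statement must be corrected, because it is the sole basis given for the sample size.

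**What to change.** Keep 80 patients and correct Section 9:

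- State that 36 evaluable per arm gives about 70% power for 11.2 points at two-sided 0.05, or 80% power for 12.7 points (t test; 12.5 by the normal approximation).
- State that 19 is a baseline SD, and name the analysed quantity (week-8 score or change) that it is assumed to describe.
- State which calculation produced 40 per arm, and repeat the sidedness in Section 16.

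This is rewording only. It needs no extra patients and no change of analysis; the cost is a less favourable power statement.

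If the sponsor prefers to claim 80% through a baseline-adjusted analysis, Section 9 must state the assumed correlation. With SD 19 at both visits, 0.5 gives about 81% by t test at 36 per arm, and about 0.48 is the minimum. Section 16 must then make that model the primary analysis, so this route also costs a change to the analysis plan. Keeping 80% for 11.2 points with SD 19 and no adjustment would require 104 (normal) or 106 (t) patients in total.

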10. INCLUSION/EXCLUSION CRITERIA

a. Inclusion Criteria

- a) Subjects aged between 18 and 80 years of age at enrolment
- b) Reporting intermittent or persistent shoulder pain for at least 6 weeks, and/or present at least 50% of the time in the past 6 months
- c) Lack of visual/audio or cognitive impairment interfering with the ability to understand or comply with the program

b. Exclusion Criteria

- a) Non-English speaking
- b) Residing outside greater SF area
- c) Known pregnancy
- d) Submitted to spinal surgery less than 3 months ago
- e) Symptoms and/or signs indicative of possible infectious disorder
- f) Referred pain from spine and/or thoracic outlet syndrome
- g) Active cancer diagnosis or undergoing treatment for cancer
- h) Cardiac, respiratory or other known disorder incompatible with at least 20 minutes of light to moderate physical activity
- i) Concomitant neurological disorder (e.g. stroke, multiple sclerosis, Parkinson's disease)
- j) Dementia or psychiatric disorders precluding patient from complying with a home-based exercise program
- k) Illiteracy and/or serious visual or auditory impairment interfering with communication or compliance

Additionally, any patient undergoing a PT program for shoulder pain will be required to stop ongoing programs to enroll in the study.

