additional benefit when utilized in conjunction with therapeutic exercise programs.³¹ This suggests that the exercise component of PT is fundamental in the treatment of painful shoulder disorders.

Regarding rehabilitation setting, some studies show that home-based therapy, based on exercise, could be as effective as conventional PT interventions.^{32,33} This is in line with the recent trends in healthcare delivery, moving away from inpatient care and towards home-based care with the intent of improving cost-effectiveness. Furthermore, the need for home-based digital solutions is now felt more acutely than ever, in the face of the current pandemic.^{34–36} In this context, solutions enabling home-based rehabilitation without requiring real-time human supervision can be key to improving effectiveness and lowering costs, while keeping all stakeholders safe. Indeed, there are studies demonstrating the potential^{37–39} and cost-effectiveness⁴⁰ of shoulder postoperative care and rehabilitation through telehealth solutions.

However, while evidence is growing that digital therapeutics (DTx) can improve outcomes, personalize care and decrease costs,⁴¹ there is still much ground to be explored in the field of digital therapy following RCR.^{42,43} Several studies can be found on the validation/development of systems/algorithms for monitoring shoulder motion to assist clinicians on patient evaluation^{44,45} but these do not meet the aforementioned needs and cannot be considered digital therapeutics.

There have been some advances on new technologies for shoulder rehabilitation, namely using wearable sensors⁴³ and augmented reality.⁴⁶ Of note, some of these studies focus on systems based on inertial motion trackers that can be used by the patient at home, under remote monitoring from the physical therapist. However, these are either in very preliminary stages of development or validation,^{47–51} with no clinical validation studies performed, or are directed at rehabilitation after stroke.^{43,46}

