5. STUDY OBJECTIVE

To assess the clinical outcomes of a digital program for chronic shoulder tendonitis versus conventional. PT.

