11. CANDIDATE IDENTIFICATION AND PROCEEDINGS

Patient recruitment will primarily be done through the use of UCSF electronic health record (EHR) recruitment services from the Clinical and Translational Service Institute (CTSI) to assist with targeting and identification of potentially eligible participants. As an "honest broker" of the EHR data, the service is designed to protect patient privacy and offer more efficient way to recruit eligible participants that meets the study's inclusion/exclusion criteria. The cohort of patients scheduled to receive physical therapy services will be identified and pre-screened by CTSI to ensure potential participants are eligible to meet the initial study's criteria. Once patients have been identified, they are flagged from their appointments for physical therapy services at the UCSF Outpatient Faculty, and will be evaluated in-person as part of their regular initial scheduled visit (i.e. evaluation visit). At the time of this visit, potential participants will be assessed by one of the co-investigators to also ensure that participants meet the cognitive and mental capacity

requirements. Once the criteria are met, investigator will present the study and invite the patient to participate and provide consent. The participant's screening survey data will be collected and be randomized to one of the two arms, coordinated by the study coordinator. All study-related information will be stored by electronic data capturing (EDC) system.

To centralize all study-related information, a commercially available electronic data capturing (EDC) system will be used.

Following the identification of a potential candidate, the investigator will enter the EDC portal and fill the screening survey. If the patient is eligible (i.e. meets inclusion criteria and does not have any exclusion criteria) the investigator will present the study and invite the patient to participate and provide consent.

12.PROCESS OF CONSENT

The study will be presented verbally to potential participants by a study investigator, in a face-toface meeting. Adequate time will be allowed for the candidate to clarify any doubts about the study, following which the eConsent form will be sent through the EDC platform to the participant and investigator, for signature. The study consent form (Annex 1) will then be signed by the participant and the investigator collecting consent, and stored in the EDC platform.

13. Allocation & Blinding

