15. PARTICIPANT ASSESSMENTS

Patients will be assessed at baseline, 4 and 8 weeks.

Baseline Assessment

This assessment will involve a face-to-face visit, where the following information will be collected:

- a) date of birth
- b) gender
- c) height & weight
- d) body mass index
- e) formal education (years of schooling)
- f) job type
- g) previous shoulder surgery (> 3 months ago)
- h) Working status
- i) Geocodes/zip
- j) Race/ethnicity
- k) Age

The following outcomes will also be assessed in this visit: a) Shoulder Range of Motion; b) PROMIS CAT measures.

Shoulder Range of Motion will be measured in the following movements: 1) shoulder flexion; 2) shoulder abduction; 3) external rotations with shoulder abducted at 90 degrees. The participant will be asked to perform three non-painful repetitions of each movement, in a standing position. The investigator will measure the maximum joint angle attained by the participant, using a digital goniometer in each repetitions. The highest of the three values will be considered.

Regarding satisfaction with social role and ability to participate in social roles and activities, these will be collected through PROMIS CAT v2.0. These will be collected onsite, and the results will then be transferred by the investigator to the eCRF.

Assessment of primary outcome, as well as the remaining secondary outcomes will be performed through an electronic questionnaire to be filled by participants, through the EDC system. These will need to be filled within 5 consecutive days, counting from the date they are sent to the participant. To promote compliance with this schedule, whenever the deadline is approaching, automatic email reminders will be sent to participants. Participants will be excluded from the study

for protocol breach in case they don't fill in the assessment forms. Upon completion of the baseline form, participants in the study will receive a stipend of \$25.

Additional measurements of upper limb function and tri-dimensional motion will also be performed at the onsite visit by the clinician, using a motion capture system. These will not be considered in the outcomes of this study, but will be made available for post-hoc analysis.

Interim assessment (4 weeks)

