ANNEX 2- DIGITAL THERAPEUTIC EXERCISE PROTOCOL

Should	ler Pain Exercise Protocol	. Phase 1 (week 1)
Goals		Precautions
Recovery of full range of motion (passive and active) Decrease pain and inflammatory signs Gradually increase muscular strength		Do not perform loaded exercises above 70° flexion / abduction
	Intervention	
	Daily Digital Therapis	t Sessions
	Remote session – Assessn	nent/Deploy
Digital Therapist Exercises	Mobility	Strength 1 (External Load – RPE >8)
	Standing Positio)n
Shoulder Flexion	2 sets of 8 reps (alternating)	2 sets of 8 reps (2/5 lbs.) (alternating)
Shoulder Hyperextension	2 sets of 8 reps (alternating)	
Shoulder Abduction	2 sets of 8 reps (alternating)	2 sets of 8 reps (5/7 lbs.) (alternating)
Scapular Plane Elevation	2 sets of 8 reps (alternating)	2 sets of 8 reps (2/5 lbs.) (alternating)
Diagonal 1 Flexion		
Diagonal 2 Flexion	2 sets of 8 reps (alternating)	2 sets of 8 reps (2/5 lbs.) (alternating)
Shoulder External Rotation	2 sets of 8 reps (alternating)	2 sets of 8 reps – Theraband (alternating)
Shoulder Internal Rotation		
Hand to Back	2 sets of 8 reps (alternating)	
Shoulder Horizontal Abduction		2 sets of 8 reps (alternating)
Shoulder Horizontal Adduction		

Shoulder External Rotation in Abduction		3 sets of 8 reps (5/7 lbs.) (alternating)
Shoulder Internal Rotation in Abduction		
Scapulae Retraction with Shoulder Flexion	2 sets of 8 reps (alternating)	
Scapulae Protraction with Shoulder Flexion		
Arm Circles with Shoulder Flexion		
Arm Circles with Shoulder Abduction		2 sets of 8 reps (2/5 lbs.) (alternating)
Chair Press-Up		
Push-Up Against the Wall		
Pendulum		
Estimated Therapy Time	20 min	20 min

Sh	oulder Pain Exercise	e Protocol. Pha	nse 1 (weeks	2 to 4)
Goals			Precautions	
Recovery of full range of motion (passive and active) Decrease pain and inflammatory signs Gradually increase muscular strength		Do not per	form loaded exercises above 70° flexion / abduction	
]	Intervention		
		ital Therapist S		
	4-Week	Remote Assess		1
Digital Therapist Exercises	Mobility	Strength 1 Load – F		Strength 2 (External Load – RPE >8)
	Star	nding Position		
Forearm Supination	2 sets of 10 reps (alternating)			
Elbow Flexion		2 sets of (alterna		
Shoulder Flexion	2 sets of 10 reps (alternating)	2 sets of 10 lbs.) (alte		
Shoulder Hyperextension	2 sets of 10 reps (alternating)			2 sets of 10 reps – Theraband (alternating)
Shoulder Abduction	2 sets of 10 reps (alternating)	2 sets of 10 lbs.) (alte		

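### Section 10 excludes recent spinal surgery but not recent shoulder surgery, so a recently operated shoulder can enter Annex 2's loaded home exercise in week 1

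*Combined protocol and SAP*

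**What the plan says.** Section 10 has eleven exclusions, (a) to (k). One concerns surgery: "Submitted to spinal surgery less than 3 months ago". Inclusion (b) opens with "Reporting intermittent or persistent shoulder pain for at least 6 weeks" and offers, as an and/or alternative, pain for at least half of the past 6 months. It does not ask for a tendonitis diagnosis and does not mention operations.

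Section 11 draws recruits from patients booked for physical therapy: "The cohort of patients scheduled to receive physical therapy services will be identified and pre-screened by CTSI". It then decides eligibility by the lists alone: "If the patient is eligible (i.e. meets inclusion criteria and does not have any exclusion criteria".

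In section 15, baseline item (g) is "previous shoulder surgery (> 3 months ago". This is a descriptive field, and it has no place for a more recent operation.

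In Annex 2, the week-1 table has a column headed "Strength 1 (External Load – RPE >8", with hand weights and Theraband. The week-1 precaution is to avoid loaded work above 70° of flexion or abduction. Phase 2 adds a precaution for complete rotator cuff tears. No phase has a post-operative precaution or variant.

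**The concern.** In a shoulder exercise trial, the operation that matters most for safety is one on the shoulder. The plan excludes recent surgery at another site and leaves the shoulder open. The 3-month limit in exclusion (d) reappears in baseline item (g), attached to the shoulder. That suggests either that one word in section 10 is wrong or that a line was left out. On either reading, sections 10 and 15 do not fit together.

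Three things are at stake:

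- **Safety.** A healing repair could be put on loaded exercise at home with no therapist in the room. Section 10 also makes patients stop any current physical therapy for shoulder pain in order to enrol, so a post-operative patient could be taken off the rehabilitation already under way. The section 17 statement that participation carries no additional risk is hard to support for such a patient.
- **Traceability.** Item (g) has no place for surgery within 3 months, so these participants could not be picked out from the baseline data.
- **Case mix.** The objective in section 5 is "To assess the clinical outcomes of a digital program for chronic shoulder tendonitis". A patient recovering from a recent repair falls outside it.

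**Working it through.** The plan gives no figure to reproduce here. The check is a reading of the eligibility rules, followed by two counts that describe the size of the gap.

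**1. Does any criterion exclude a recently operated shoulder?**

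| Criterion (section 10) | Excludes recent shoulder surgery? |
|---|---|
| Inclusion (a) age, (c) sensory and cognitive ability | No |
| Inclusion (b) pain duration | No; any cause of shoulder pain qualifies |
| Exclusions (a) language, (b) residence, (c) pregnancy | No |
| (d) surgery within 3 months | Spine only |
| (e) infection, (f) referred pain, (g) cancer, (i) neurological disorder | No |
| (h) unable to do 20 minutes of light to moderate activity | No; this is general exercise tolerance |
| (j) dementia or psychiatric disorder, (k) illiteracy or sensory impairment | No |

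Of 11 exclusions, 1 concerns surgery and 0 concern shoulder surgery. Section 11 gives the investigator no stated discretion to exclude on other grounds.

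**2. Is the post-operative patient obviously out of scope?** Not from the text. Recruits come from a physical therapy schedule, where post-operative patients are plausible, and the background presents rotator cuff repair as an area of interest: "there is still much ground to be explored in the field of digital therapy following RCR".

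**3. How wide is the gap?** Take 3 months as about 91 days: 91 / 7 = 13 weeks.

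- Pain counted only from the operation, 6-week branch of inclusion (b): weeks 6 to 13 are open. 13 − 6 = 7 weeks; 7 / 13 = 0.54.
- Pain before the operation also counts, which the text allows: all 13 weeks are open.
- Enrolment at post-operative week 6, with an 8-week program, covers weeks 6 to 14. Of those 8 weeks, 13 − 6 = 7 lie inside the 3-month window. Later enrolment gives fewer.

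**4. What load would such a patient meet by default?** Sets with a stated weight or band in the week-1 Strength 1 column of Annex 2:

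| Exercise | Sets of 8 | Load |
|---|---|---|
| Flexion | 2 | 2/5 lbs |
| Abduction | 2 | 5/7 lbs |
| Scapular plane elevation | 2 | 2/5 lbs |
| Diagonal 2 flexion | 2 | 2/5 lbs |
| External rotation | 2 | Theraband |
| External rotation in abduction | 3 | 5/7 lbs |
| Arm circles with abduction | 2 | 2/5 lbs |
| **Total** | **15** | |

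15 × 8 = 120 repetitions per session: 13 × 8 = 104 with weights and 2 × 8 = 16 with Theraband. Horizontal abduction (2 × 8) has no stated load and is left out. The table marks sets as alternating without defining the term; if repetitions are split between arms, the figure is 120 / 2 = 60 per arm.

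**The case against.** The strongest reply is that the plan is plainly meant for non-operative patients and that a clinician would catch the exception. The background stresses conservative care first, section 8.2 asks about interest in future surgery, and Annex 3 refers to chronic shoulder pain. Patients are seen in person at their initial therapy visit, where the capacity check is only an added task. Baseline testing asks for non-painful shoulder movements, including external rotation at 90° of abduction. The digital arm has an onboarding contact and a week-1 remote assessment, the therapist may adapt Annex 2, loaded work stops at 70°, and pain and fatigue are asked after every session with follow-up if excessive. Surgical history should also be recoverable from the health record.

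Much of this stands as mitigation. A recently operated shoulder would probably often be noticed, and the traceability problem concerns the trial's baseline data rather than the source records. The screening survey's items are not shown, so it may ask about surgery. But none of these steps is an eligibility rule. Intent in the background does not bar entry when section 11 decides by the lists, and therapist adaptation is optional and not tied to surgery. The 70° limit restricts range; it does not settle whether a recent repair should be loaded at all.

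It is also fair to say that the counts are not measures of risk. The 54% is a share of calendar weeks, and the 120 repetitions are the default before any adaptation. The documents do not state which RPE scale applies.

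**Conclusion.** The concern holds. Followed as written, section 10 admits a patient within 3 months of shoulder surgery, and section 15 assumes that it does not. The gap is 7 of 13 weeks if pain is counted only from the operation and all 13 if earlier pain counts. The default week-1 exposure in the digital arm is 120 loaded repetitions per strength session, or 60 per arm if alternating means split between arms.

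The conclusion rests on the wording of the criteria and needs no assumption about how many recruits are affected; the documents do not give that number. That *spinal* stands in place of *shoulder* is an inference from the shared 3-month limit and is not established. Randomisation balances such patients between arms on average, so the gap affects safety and the population to which the result applies, not the validity of the comparison. The correction should be made, but it does not threaten the primary analysis.

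**What to change.** 1. Add shoulder surgery within the past 3 months as an exclusion in section 10, in the CTSI pre-screen and in the EDC screening survey, so that eligibility agrees with baseline item (g). Asking for the date of any shoulder surgery in the screening item would make the rule checkable.
2. Check whether *spinal* in exclusion (d) was meant to be *shoulder*. If so, replace the word. If not, keep both exclusions.

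The cost is one line in section 10, one survey item and a matching pre-screen filter, with no new visits, staff or measurements. If enrolment has started, a short amendment is needed. The trial would lose recruits with recent shoulder surgery; these are probably few, though the documents give no number.
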